2.6 Treatment Allocation

Approximately 300 participants assigned to RGF who are determined eligible will be randomly allocated to one of two ABBV-CLS-7262 dosages or placebo. Approximately 165 will be randomized to ABBV-CLS-7262 administered QD at a dosage of 120 mg, approximately 60 participants will be randomized to ABBV-CLS-7262 administered QD at a dosage of 240 mg, and approximately 75 participants will be randomized to placebo. Treatment assignments are based on a pre-specified permuted-block randomization schedule stratified for all combinations of use vs. non-use of riluzole, edaravone, and sodium phenylbutyrate/taurursodiol (Relyvrio® or Albrioza®) at the time of screening for the Master Protocol. The first 240 participants will be assigned in a 2:1:1 allocation ratio to 120 mg ABBV-CLS-7262, 240 mg ABBV-CLS-7262, or placebo. The final approximately 60 participants will be assigned in a 3:1 allocation ratio to 120 mg ABBV-CLS-7262 or placebo by interpreting any assignments to 240 mg ABBV-CLS-7262 as an assignment to 120 mg ABBV-CLS-7262.

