3.2 Summary Statistics

Data will be summarized with respect to disposition, demographics, pre-treatment characteristics, efficacy endpoints, safety endpoints, and tolerability. Summary statistics for continuous variables will include the number of observations, the mean, median, standard deviation, inter-quartile range, and range. Summaries of continuous secondary endpoints will include empirical cumulative distribution functions (eCDF). Summaries of categorical data will include counts, denominators, and percentages.

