4.4 Safety Endpoints

The safety endpoints collected up to 30 days after the last dose of study drug in the RCT will be included in the safety analysis. For participants who enroll in the ATE, only safety endpoints before ATE baseline will be included. The following safety endpoints will be evaluated:

- · Treatment-emergent adverse and serious adverse events,
- Changes in laboratory values and treatment-emergent and clinically significant laboratory abnormalities,
- Changes in ECG parameters and treatment-emergent and clinically significant ECG abnormalities, and

- Changes in vital signs and treatment-emergent and clinically significant vital sign abnormalities, and
- Treatment-emergent suicidal ideation and suicidal behavior.

Reported proportions will use as their denominator all participants in the applicable Safety sample (see Section 6.1 below). Clinically significant laboratory, ECG, and vital sign abnormalities will be reported as adverse events.

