5.13 Clinical Safety Laboratory Tests

The list of clinical safety labs and the definitions of measures of potential drug-induced liver injury (DILI) are the same as described in the M-SAP with the following additional analyses:

- Digestive enzymes: amylase, lipase
- Hormones: ACTH, cortisol, total testosterone (males only), luteinizing hormone (males only)
- Thyroid function: free T4, T3
- Cosyntropin stimulation testing: abnormal response is defined as a maximum cortisol concentration less than 18 µg/dL after intravenous (IV) cosyntropin injection.

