- Safety Full (STF) Set: Participants who received at least one dose of study drug within RGF plus placebo participants from Regimens A, B, C, D, E, G who had an opportunity to complete placebo-controlled follow-up, who are not known to be ineligible for RGF, and who received at least one dose of study drug in their respective regimen, classified according to the treatment they actually received. Observations made after premature permanent discontinuation of study drug are included in this sample, should such participants remain on study. Observations completed after regimen data lock are excluded.
- Safety Concurrent Control set (SCC): The subset of participants in the STF analysis set who
 were randomized within RGF or randomized to placebo within RGG at or prior to the date
 when the last RGF participant was randomized, exclusive of RGG participants who were also
 randomized within RGF.
- Safety Narrow (STN) Set: The subset of participants in the STF analysis set who were exposed to interventions administered orally.
- Safety Regimen-only (SRO) Set: The subset of participants in the STF analysis set who were randomized within RGF.

The meaning of regimen data lock and the criteria for inclusion of data for placebo participants assigned to other regimens at the time of regimen data lock will be defined in the HEALEY ALS Platform Trial Data Management Plan and the HEALEY ALS Platform Trial Data Sharing Plan. Specifically, concurrent placebo participants from RGG randomized at or prior to the date when the last RGF participant was randomized will be included for RGF analysis.

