6.6.2 Safety Labs

Summaries of safety labs are the same as described in the M-SAP with the addition of the SCC analysis set and the addition of summaries for assays specific to RGF: amylase, lipase, ACTH, cortisol, total testosterone (males only), luteinizing hormone (males only), TSH, free T4, T3, and abnormal cosyntropin stimulation response.

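### SAP 4.4's all-participants denominator would count untested Regimen G controls as free of abnormality if Regimen F-specific assays are tabulated in the concurrent-control safety set

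*SAP*

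**What the plan says.** SAP 4.4 lists treatment-emergent and clinically significant laboratory abnormalities among the safety endpoints and then sets one denominator rule: "Reported proportions will use as their denominator all participants in the applicable Safety sample (see Section 6.1 below"). It makes no exception for participants without a result. The following sentence adds: "Clinically significant laboratory, ECG, and vital sign abnormalities will be reported as adverse events".

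The safety sets in SAP 6.1 are defined by dosing, regimen, randomization, route, eligibility and opportunity for follow-up. None requires an assay result, and none restricts by sex. SCC takes those who "were randomized within RGF or randomized to placebo within RGG at or prior to the date" of the last Regimen F randomization. The regimen-only set is "Safety Regimen-only (SRO) Set: The subset of participants in the STF analysis set who were randomized within RGF".

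SAP 6.6.2 keeps the M-SAP laboratory summaries and makes two additions in one sentence: the SCC set, and "the addition of summaries for assays specific to RGF: amylase, lipase, ACTH, cortisol, total testosterone (males only"), with LH (also males only), TSH, free T4, T3 and cosyntropin response following. SAP 5.13 carries the same label: "Hormones: ACTH, cortisol, total testosterone (males only), luteinizing hormone (males only").

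In the protocol (RSA), Section 6 lists amylase, lipase and the hormone laboratory tests as additions to the Master Protocol procedures, and the Schedule of Activities marks hormone assessments as a regimen item.

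**The concern.** The word applicable in SAP 4.4 points to Section 6.1, so it selects a safety set and not the tested participants within it. For an assay run in everyone, that hardly matters. For an assay run in one regimen only and tabulated in a set that borrows controls from another, it does: a borrowed control who was never tested adds one to the placebo denominator and can never add to the numerator. The placebo percentage falls, and the drug looks worse than it is.

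These assays are in the trial because of animal findings. RSA 1.1 describes adrenal, reproductive-organ and pancreatic effects, and RSA 5.10 adds the hormone and digestive-enzyme tests on that basis. The comparison with placebo in these tables should therefore be readable at face value. SAP 3.2 says "Summaries of categorical data will include counts, denominators, and percentages", but under SAP 4.4 the printed denominator is the size of the set, so it would not show how many were tested.

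Testosterone and LH raise a second question. Both are labelled males only, while the denominator rule has no sex restriction. A programmer following SAP 4.4 and one following SAP 6.6.2 could produce different percentages from the same data.

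**Working it through.** **Group sizes (SAP 2.6; SAP Appendix 1, 3.1).** The plan's figures reproduce:
- Regimen F placebo: 240 × 1/4 + 60 × 1/4 = 75.
- 120 mg: 240 × 2/4 + 60 × 3/4 = 165.
- Concurrent controls: 75 + 60 = 135, as stated in Appendix 1. The 60 Regimen G controls are a simulation assumption. SCC admits only those randomized by the date of the last Regimen F randomization.

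**Shared-control dilution.** Let C be the number of Regimen G controls in SCC and f the fraction of them tested. Assume that everyone in Regimen F is tested and that the true abnormality rate is the same in all groups. The displayed placebo rate is then the true rate × (75 + fC)/(75 + C), and the spurious drug/placebo ratio is (75 + C)/(75 + fC).

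| f | C = 60: ratio | True 10% placebo rate reads | C = 30: ratio | True 10% placebo rate reads |
|---|---|---|---|---|
| 0 | 135/75 = 1.80 | 5.6% | 105/75 = 1.40 | 7.1% |
| 0.25 | 135/90 = 1.50 | 6.7% | 105/82.5 = 1.27 | 7.9% |
| 0.50 | 135/105 = 1.29 | 7.8% | 105/90 = 1.17 | 8.6% |
| 0.75 | 135/120 = 1.13 | 8.9% | 105/97.5 = 1.08 | 9.3% |
| 1 | 135/135 = 1.00 | 10.0% | 105/105 = 1.00 | 10.0% |

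C = 30, the values of f and the 10% rate are assumptions. The documents give neither f nor an event rate.

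**Regimen-only set.** In SRO, C = 0 and the ratio is 75/75 = 1.00, so there is no shared-control dilution.

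**Missing results within Regimen F.** Appendix 1 assumes 2% non-mortality dropout per month, and the first post-baseline draw is at Day 28. Loss before it is 1 − 0.98^(28/30.44) = 1.8%, so a true 10% reads about 9.8%. This is negligible, and ordinary missing data are not the issue.

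**Which assays.** Amylase, lipase, ACTH, cortisol, testosterone and LH are the clear candidates. Thyroid function is part of the clinical safety labs, which the Schedule of Activities marks as a Master item, so TSH may well exist in shared controls. SAP 5.13 lists free T4 and T3 as additions to the M-SAP panel, so their status is uncertain.

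**Males-only assays.** If the SAP 4.4 rule is read literally, displayed rate = rate in males × male share. The male share is not in the documents. At an assumed 50% to 65%, a true 10% among males reads 10% × 0.50 = 5.0% to 10% × 0.65 = 6.5%, and this applies in every arm, including in SRO.

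**The case against.** The strongest reply is that neither the tables nor the untested controls are visible. SAP 6.6.2 defers to the M-SAP for the form of the laboratory summaries, and the M-SAP is not available; it may call for visit summaries, shift tables or per-assay counts. The sentence in 6.6.2 names SCC and the Regimen F assays as separate additions and does not expressly say that the second will be tabulated in the first. Whether Regimen G ran these assays is not stated. All of this stands, and it is why the point is conditional and its lower bound is no bias at all. It does not remove the point: no visible passage overrides SAP 4.4 or confines these assays to SRO, and SAP Section 1 makes the R-SAP prevail where it differs from the M-SAP.

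An all-treated denominator is also the usual choice for adverse events, and clinically significant laboratory abnormalities are reported as adverse events. That is right, and the rule should stay for them. The number of observations in the continuous summaries would also let a careful reader see that controls were untested, although the percentage itself would remain wrong.

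Three stronger readings are tempting, and the documents do not support them:
- **That the plan intends to count females as non-events for testosterone and LH.** It does not say so. The males-only label sits in the sections that define these tests and summaries (SAP 5.13 and 6.6.2) and can fairly be read as restricting them already. What exists is a conflict with the general sentence in 4.4.
- **That counting females would bias the arm comparison**, because the "permuted-block randomization schedule stratified for all combinations of use vs. non-use of riluzole, edaravone" and other ALS treatment does not include sex. Any imbalance would be chance variation around a ratio of about 1. The level is understated in every arm, but the ratio is not systematically shifted.
- **That the rule could hide a safety signal against placebo.** Untested controls lower the placebo rate, so the distortion runs against the drug.

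**Conclusion.** The point holds as a minor one. SAP 4.4 sets an unqualified denominator, and SAP 6.6.2 brings in both a set with borrowed controls and assays specific to Regimen F. Followed as written, and if abnormality proportions for those assays are tabulated in SCC, the rule treats untested Regimen G controls as normal. The spurious drug/placebo ratio lies between 1.00 and 1.80 with 60 Regimen G controls, and between 1.00 and 1.40 with 30. A reader might take 1.80 as the expected error. It is the extreme case, needing all 60 simulated controls to be concurrent and none of them tested.

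Continuous summaries are unaffected. No visible passage bases a hypothesis test or decision rule on these proportions. The full (STF) and oral-only (STN) safety sets also include shared placebo participants, but whether their laboratory tables are affected depends on the M-SAP.

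On testosterone and LH the finding is a conflict between SAP 4.4 and SAP 5.13 and 6.6.2 that needs reconciling. If 4.4 were followed literally, rates would be scaled down by the male share in every arm.

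**What to change.** In SAP 4.4, state that proportions of laboratory abnormalities use as denominator the participants in the set with at least one post-baseline result for that assay, males only for testosterone and LH, and that this number is shown per arm. This also settles the conflict with SAP 5.13 and 6.6.2.

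In SAP 6.6.2, present the Regimen F-specific assays in SRO alongside SCC, and rely on SRO where few or no shared controls were tested.

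Keep the all-participants denominator for adverse events. Add a footnote that adverse events arising from Regimen F-specific assays could not be detected in shared controls who did not have the test.

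The cost is two or three sentences of SAP wording and one footnote. The downside is slightly more table programming and denominators that vary by assay. Data collection and the efficacy analyses do not change.

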4.5 Study Comparisons

The primary comparison of interest is between the ABBV-CLS-7262 120 mg dosage group and the shared concurrent placebo group when evaluating primary, secondary, and exploratory endpoints. Comparisons involving the ABBV-CLS-7262 240 mg dosage group and comparisons other than the primary comparison of interest are exploratory. Dose-dependent contrasts are of primary interest for pharmacokinetic endpoints.

5. Measurement Definitions

5.1 ALSFRS-R

The definition and scoring of the ALSFRS-R are the same as described in the M-SAP.

5.2 SVC

The definition and quantitation of SVC are the same as described in the M-SAP.

5.3 HHD and Grip Strength

The definition and quantitation of HHD and grip strength are the same as described in the M-SAP.

5.4 Biofluid Biomarkers

The definition and quantitation of serum NfL and serum creatinine are the same as described in the M-SAP with the following modifications. Serum NfL concentrations will be estimated from baseline serum samples twice. The first analysis of baseline serum samples for quantitation of serum NfL will be completed late enough to include baseline serum samples from all participants who will be included in the primary efficacy analysis for RGF and early enough that results from that analysis will be available at the time of database lock for clinical data from the 24-week placebo-controlled period. Serum NfL concentrations estimated from this first analysis will only be used as a covariate in analyses that include baseline serum NfL as a covariate. The second analysis of baseline serum samples for quantitation of serum NfL will be completed in combination with all other available serum samples collected during the 24-week placebocontrolled follow-up of participants who will be included in the primary efficacy analysis for RGF. All samples from a given participant in this second analysis will be analyzed on a single plate to minimize potential batch effect and serum NfL concentrations estimated from this second analysis will be used to estimate longitudinal changes in serum NfL as an efficacy endpoint. If baseline serum NfL concentrations for a given sample are not the same between the two analyses, they will be handled separately based on the above descriptions.

The following regimen-specific biomarkers will be assayed: plasma NfL, CSF NfL, CSF GDF-15, CSF FGF21, and urinary p75^{ECD}. Plasma NfL, CSF NfL, CSF GDF-15, and CSF FGF21 will be quantified by automated chemiluminescent enzyme immunoassay (LUMIPULSE G System, Fujirebio, Malvern, PA). Urinary p75^{ECD} will be assayed following Shepheard et al. (2022). Concentrations will be normalized to urinary creatinine concentration measured in the same sample and expressed as ng p75^{ECD} per mg creatinine. Following Shepheard et al. (2022), urinary p75^{ECD} from samples with urinary creatinine less than 0.3 ng/mL or greater than 3.0 ng/mL will be excluded from analysis.

5.5 Patient-reported Outcomes

5.5.1 ALSAQ-40

The Amyotrophic Lateral Sclerosis Assessment Questionnaire (ALSAQ-40, Jenkinson et al. 1999; Jenkinson et al. 2003) is a 40-item ALS-specific health-related quality-of-life instrument completed by participants for assessing quality of life in five domains: physical mobility (10 items), independence in activities of daily living (10 items), eating and drinking (3 items), communication (7 items), and emotional reactions (10 items). For each item, participants are asked to rate the degree to which a specific statement describing difficulties of living with ALS applies to the participant's personal experience over the past two weeks on a 5-point scale from 0 ("Never") to 4 ("Always").

The total score will be calculated as the mean of all 40 items multiplied by 25 (range 0 to 100). Each of the five domains will be scored as the mean of all domain-specific items multiplied by 25 (range 0 to 100). The total score and each domain score will be missing if more than 20% of the applicable items are missing; otherwise, item non-response will be mean-imputed from other completed items from the same assessment. Higher scores indicate worse quality of life.

5.5.2 CNS-BFS

The Center for Neurologic Study Bulbar Function Scale (CNS-BFS, Smith et al. 2018) is a 21-item instrument completed by participants for assessing bulbar function in three domains: speech, swallowing, and sialorrhea. For each domain, participants are asked to rate the degree to which each of seven statements describing an aspect of bulbar dysfunction apply to the participant's personal experience over the past week on a scale from 1 ("Does not apply") to 5 ("Applies most of the time"). Subjects unable to speak are assigned a value of 6 for each item comprising the speech domain. The total score is the sum of all items (range 21 to 112). Higher scores indicate worse bulbar dysfunction.

5.5.3 ROADS

The Rasch-built Overall ALS Disability Scale (ROADS, Fournier et al. 2020) is a 28-item instrument completed by participants for assessing overall functional disability associated with ALS. Each item assesses the participant's ability to perform a stated task on a scale from 0 ("unable to perform") to 2 ("normal"). Participants are instructed to rate their ability based on how a given task is usually performed; items should be scored as 2 (normal) if the task is performed as quickly and easily as it was before experiencing symptoms of ALS; items should be scored as 1 (abnormal) if it is harder to perform the task, the task takes more time or effort, or the task is performed with the assistance of a device or another person. The sum of the item scores is normed to a linearly-weighted total score (range 0 to 146). Higher scores indicate better function.

5.6 Survival

The definition of the survival endpoints of death or death-equivalent and death-only for the placebo-controlled period are the same as described in the M-SAP.

5.7 King's ALS Clinical Staging System

The definition and scoring of the King's ALS Clinical Staging System are the same as described in the M-SAP with the addition of a fifth stage indicating death. Participants who die or reach a death equivalent will be assigned to stage 5.

5.8 Quantitative Voice Characteristics

Voice samples will be collected using the Aural Analytics app installed on either an Android or iOS-based smartphone. At each assessment, participants perform a set of speaking tasks: reading 5 prespecified sentences, reading 5 sentences chosen at random from a large sentence bank, repeating a consonant-vowel sequence, producing a sustained phonation, and counting on a single breath. Speech analysis will be performed by Aural Analytics to derive the following quantitative voice characteristics: maximum phonation time, pause rate, breathy vocal quality, pitch instability, regulation of voicing, articulatory precision, speaking rate, articulation rate, and monotonicity.

5.9 Hospitalization and Other Clinical Events

Times to the following clinically relevant events are defined:

- Time to first hospitalization due to a serious adverse event (SAE),
- Time to first hospitalization due to an ALS-related SAE,
- Time to first use of assisted ventilation,
- Time to first placement of a feeding tube, and
- Time to King's stage 4a or 4b.

Time at risk for each event will be measured from each participant's Baseline Visit. Time to first hospitalization excludes hospitalizations for elective procedures. ALS-related SAEs are those indicated as related to ALS disease progression by the site investigator. Participants who are already using assisted ventilation or have a feeding tube at the time of the Baseline Visit will be excluded from analysis of those endpoints. Death or death equivalent will be considered an outcome for each of the events listed, forming a composite endpoint.

Time at risk for these events will be censored at the Week 24 Visit, if completed, the date of consent withdrawal, if withdrawn, or the last date at which the status of each endpoint is known prior to the end of the Week 24 Visit window for participants lost to follow-up. Time to King's stage 4a or 4b is interval censored between ALSFRS-R assessments.

5.10 TRICALS Risk Profile

The Treatment Research Initiative to Cure ALS (TRICALS) Risk Profile is based on the the European Network for the Cure of ALS (ENCALS) survival prediction model (Westeneng et al. 2018). The TRICALS score will be calculated at baseline as follows:

Profile =
$$0.474[(VC/100)^{-1} + (VC/100)^{-1/2}] - 2.376[(DD/10)^{-1/2} + ln(DD/10)]$$

- $1.839(dFRS + 0.1)^{-1/2} - 0.264(AAO/100)^{-2} + 0.271$ Bulbar
+ 0.238 Definite + 0.415 FTD

where VC is vital capacity in units of percent-predicted using GLI norms as defined in Section 5.2, DD is diagnostic delay calculated as (date of diagnosis – date of symptom onset) / 365.25 x 12, dFRS is pre-baseline slope of ALSFRS-R total score as defined in Section 5.1, AAO is age at symptom onset calculated as (date of symptom onset – date of birth) / 365.25, Bulbar is an indicator of initial site of onset in the bulbar region, Definite is an indicator for classification as definite ALS by revised El Escorial criteria, and FTD is an indicator for frontotemporal dementia. While participants are not evaluated for frontotemporal dementia at baseline, given that presence of dementia defined broadly is an exclusion criterion at screening, TRICALS scores will be calculated assuming that participants do not have frontotemporal dementia.

